2.6 Population

Subjects will be healthy controls.

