4.2 Trial Design

Overall:

This study will initially utilize DaTSCAN and fMRI in healthy subjects within one month of entering a meditation retreat program. In addition, they will complete a variety of questionnaires and scales to assess their psychological status. They will then undergo the retreat and will return within one week of completing the retreat to repeat the scans and questionnaires. Thus, they will receive 2 DaTSCAN scans and 2 fMRI scans over the course of the study.

Time	Procedure
09:00 a.m.	Subject arrival. Review informed consent procedures.
09:30 a.m.	beta-HCG (if necessary)
09:45 a.m.	SSKI (Lugol's solution)
10:00 a.m.	Insert i.v. catheter
10:15 a.m.	Inject DaTSCAN
11:00 a.m.	Subject may take a break for 4 hours during which several
	qualitative scales will be performed
01:15 p.m.	Begin SPECT imaging
02:15 p.m.	SPECT scan completed
02:30 p.m.	Study completed

Approximate Timeline for DaTSCAN SPECT

Medical assessment procedures. A trained physician will take a detailed medical history on each subject and perform a standardized review. Structured physical, neurological, and psychological examinations will be performed. A set of clinical laboratory studies may be used to screen potential subjects with benign histories and normal physical examinations. A urine test for pregnancy will be performed in all women of childbearing potential. Female subjects with negative pregnancy tests will be enrolled.

Quantifying subjective phenomena. This protocol will add the administration of a number of neuropsychological tasks, psychological inventories, and spiritual scales at the time of imaging. These tests and questionnaires should take approximately two hours to complete, and many have already been widely used in both control and patient populations. These well established tests

were originally validated in large populations of people, and have since been used extensively in both clinical and research settings. Our lab has its own normative data base, which has been generated for people of all age ranges. The battery may include the following tests:

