The reference region has typically been the cerebellum because this region has such low activity on ¹²³I DaTSCAN scans and no appreciable DAT or SERT receptors. However, values will be obtained for both whole brain regions above the basal ganglia and cerebellar regions in order to confirm the findings. The procedures will be implemented with a commercial statistical package (StatS, Think Point Software, Inc). The reliability of SPM will be evaluated similarly by having two different technicians run the analyses independently. We have found the reliability of the image analysis techniques to be high with intra-class correlations consistently above 0.95.

c) MR image acquisition: Subjects will be studied to evaluate the effects of the meditation retreat program on cerebral activity using fMRI. This approach will enable us to track changes and activation in cerebral activity that result from the program. This data will be correlated to standardized neuropsychological and behavioral measures of cognition, mood, and spirituality.

The fMRI images will be co-registered and comparable slices of the cerebral cortex will be examined pre and post program. We will evaluate changes in baseline brain function while the subject is at rest as well as during the meditation practice itself. Two different analysis approaches will be used since they can provide different types of information. A region of interest analysis will be performed to assess changes of activity in specific brain regions. A comparison between meditation and baseline cerebral activity will indicate which regions of the brain are activated at various stages of meditation.

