4.8 Randomization Codes

Since this is a diagnostic study, subjects are not randomized.

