8.4 Type and Duration of Follow-up of Subjects After Adverse Events

Subjects will be followed six months after the injection if they experienced an adverse event directly related DaTSCAN. If there is no further problem, this will terminate the follow up. However, if the subject continues to have problems directly related to the DaTSCAN, then they will continue to be followed at six months intervals until the adverse event resolves or until the subject's death.

9. Statistics

9.1 Description of Statistical Methods Region of Interest Analysis.

The images of each of the scans will be reconstructed and resliced, using an oblique reformatting program, according to the anterior-posterior commissure line. The SPECT images will be co-registered with the anatomical MRI and comparable slices of the cerebral cortex will be examined. A previously validated template methodology consisting of regions of interest (ROI) corresponding to the major cortical and subcortical structures will be placed over the scans (Resnick 1993). For the purposes of this study, we will examine the regional CBF, serotonin transporter and dopamine transporter activity in only a selected number of ROIs which will be hypothesis driven. The ROIs to be examined based on the hypotheses described above and the preliminary findings will be the inferior frontal, superior frontal, dorsolateral prefrontal, orbitofrontal, dorsal medial cortex, inferior temporal, amygdala, hippocampus, superior parietal, inferior parietal, occipital, and sensorimotor areas, as well as the caudate, putamen, thalami, midbrain, hypothalamus, cerebellum, and cingulate gyrus regions. Each ROI will have its placement adjusted manually in order to achieve the best fit according to the atlas. The ROIs will then be copied directly onto each of the scans. This will be possible because the images will

already resliced into the same planes as described above. Counts will be obtained for each ROI and normalized to the mean whole brain counts. This will result in ratios of activity in each ROI will be compared across scans for each neuropsychological state. Other covariables such as age, and psychological measures, can also be included in the statistical analysis. The cerebral structures will be identified by their Talairach coordinates (Talairach 1988).

Statistical parametric mapping (SPM):

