Groups of images will be compared voxel-by-voxel using SPM (Friston 1995). Statistically significant differences between sets of data will be assessed at each voxel with a threshold of P < 0.001. To correct for correlated multiple comparisons, clusters of voxels which survive this threshold will be assessed further using the theory of random Gaussian fields (Friston 1994, 1995b; Worsley 1994), which calculates the significance of clusters based on their peak height and spatial extent. With this technique, differences in blood flow between and within groups will be assessed, and statistic images generated showing significant regional differences between groups. The meditation or activation state can be modeled by a simple one-way analysis of covariance (ANCOVA) with a group effect (the activation) combined with a nuisance or confounding effect (global or reference region activity) to produce the observed data. Other covariables such as age, and psychological measures, can also be included in the statistical

analysis. The cerebral structures will be identified by their Talairach coordinates (Talairach 1988).

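### Section 4.2(c) attributes fMRI changes to the retreat, but one cohort scanned once before and once after cannot separate retreat from repeat-session or time effects, and no test compares the meditation-minus-rest difference before and after

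*Combined protocol and SAP*

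**What the plan says.** **Causal wording.** The MR paragraph of 4.2 (item c) presents the fMRI work as evaluating the effects of the retreat and continues: "This approach will enable us to track changes and activation in cerebral activity that result from the program". Objectives 1 and 3 (section 3) and the endpoints (4.1) are more modest. They speak of association and of comparing pre with post.

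**Design.** Section 2.6: "Subjects will be healthy controls". Section 4.8: "Since this is a diagnostic study, subjects are not randomized". Section 4.2: "Thus, they will receive 2 DaTSCAN scans and 2 fMRI scans over the course of the study". The first session falls within a month before the retreat. For the second: "They will then undergo the retreat and will return within one week of completing the retreat to repeat the scans and questionnaires". No waiting-list group, unexposed group or second baseline session is defined. Section 4.2 also allows other activities or practices between the scans.

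**States measured.** Section 4.2(c): "We will evaluate changes in baseline brain function while the subject is at rest as well as during the meditation practice itself". The same paragraph plans a comparison of meditation with baseline, whose stated use is to show which regions are activated.

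**Analysis.** In the region-of-interest (ROI) part of 9.1, counts are normalised to the whole-brain mean and then "ratios of activity in each ROI will be compared across scans for each neuropsychological state". In the SPM part, "differences in blood flow between and within groups will be assessed", at a voxel threshold of 0.001 with cluster-level correction, and an ANCOVA with global or reference-region activity as a nuisance term is offered. Section 9.3 sets 0.05 for all statistical measures.

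**The concern.** The retreat always lies between session 1 and session 2, so before/after and first/second session are the same variable. Familiarity with the scanner, expectation, regional signal differences between sessions, the passage of time and other activities between scans all fall into the pre/post difference together with any retreat effect. The wording of 4.2(c) assigns that difference to the program.

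There is a second, smaller gap. Rest and meditation are each to be examined for change, but no test sets the two changes against each other. If one state changed significantly and the other did not, it would be easy to report that the response to meditation had changed, although that difference had never been tested.

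At stake is a causal sentence about brain activity, carried into publication from a design that supports only a before/after description.

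**Working it through.** **1. What the design identifies.** For one region and one state, write the expected pre-to-post change as *R + S*, where *R* is the retreat effect and *S* is the session or time shift in the normalised measure. Every subject has the retreat between the two sessions, so the data estimate only the sum. Normalising to the whole-brain mean removes a shift that scales all regions equally. It leaves a shift that differs by region. Blinded reading (4.3) does not separate the two terms.

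**2. Inputs.**
- Change 10%, SD 15%, n = 25: section 9.2. Section 9.4 also gives 25 subjects; 5.1 allows up to 30.
- Two-sided 0.05 for ROI tests: 9.2 and 9.3. Voxel threshold 0.001: 9.1, taken here as two-sided.
- Size of *S*: not in the documents. The range below is assumed.
- Correlation between the rest change and the meditation change: not in the documents. The range below is assumed.

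**3. The plan's own figure.** Section 9.2 states 80% power with 25 subjects in a two-group t-test. With 10/15 = 0.667 SD, that test needs 37 per group (exact t), and 25 per group gives 64%. A paired test with 15% as the SD of change gives 89% at n = 25. The stated figure does not reproduce under either reading. That is a separate matter, and the present point does not depend on it. I take 15% as the SD of change because the comparison is within subject. Section 9.2 draws the figure from other neuropsychological-state and transporter-binding work, so using it for fMRI is a further assumption.

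**4. Chance of a significant result with *R* = 0.** Paired t-test, 24 degrees of freedom, noncentrality = (*S*/15) × √25 = *S*/3. The critical value is 2.064 at 0.05.

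| Assumed regional shift *S* | Noncentrality | P(significant), ROI test at 0.05 |
|---|---|---|
| 0% | 0 | 5.0% |
| 2% | 0.67 | 9.8% |
| 3% | 1.00 | 16.1% |
| 5% | 1.67 | 36.0% |

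With n = 30 the 5% row becomes 42%. At the voxel threshold of 0.001 (critical value 3.745) a 5% shift is flagged 3.6% of the time at a given voxel, before cluster correction.

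**5. The comparison the collected data allow.** Per subject, take (meditation − rest, post) − (meditation − rest, pre). If the session shift is *S*_M in the meditation run and *S*_R in the rest run, the session part of the contrast is *S*_M − *S*_R. It is zero only when the shift is common to both runs.

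If each state's change has SD 15% and the two changes correlate ρ, the SD of the contrast is 15 × √(2(1 − ρ)). At n = 25, two-sided 0.05:

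| ρ (assumed) | SD of contrast | Power for a 10% meditation-specific difference | P(significant) if *S*_M − *S*_R = 5 points and there is no retreat effect |
|---|---|---|---|
| 0 | 21.2 | 62% | 20% |
| 0.25 | 18.4 | 74% | 26% |
| 0.5 | 15.0 | 89% | 36% |
| 0.75 | 10.6 | 99.5% | 62% |

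With a common shift the error rate stays at 5% for every ρ. With a shift that differs between runs it does not, so the contrast supports a description and cannot restore the causal claim.

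**The case against.** The case against making much of this has real force.

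- The study is declared exploratory (9.2), its primary outcome is SERT and DAT binding (4.2(b)), and the objectives already use associational language. All true. It justifies a small uncontrolled study, but not the causal wording of 4.2(c).
- A reader might infer that every first-to-second-session shift is counted as a retreat effect. The documents do not support that. Whole-brain normalisation and the optional nuisance covariate in 9.1 deal with purely global shifts, so the concern is limited to regional ones.
- A reader might infer that the first scan is the only comparator. It is not: 4.2(c) plans a meditation-versus-baseline comparison. But its stated use is to locate activation, and no passage compares it between sessions.
- A reader might take the between-groups wording in 9.1 as evidence of a missing control cohort. The SPM text speaks of groups of images and treats the activation as the group effect, so it plausibly means sets of images. Deleting 'between' could remove an intended comparison.
- The phrase about each neuropsychological state in 9.1 may mean pre and post rather than rest and meditation. The plan is therefore unspecific about the contrast. It does not exclude it.
- The magnitude rests on an assumed shift, and the 36% applies to ROI tests at 0.05, not to the voxel maps. Both points stand.

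**Conclusion.** The point holds in a limited form. Section 4.2(c) claims that the fMRI changes are produced by the program. The design supports only pre-to-post change associated with taking part, which is what Objectives 1 and 3 ask for. This follows from the design and needs no numerical assumption.

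The size is illustrative. If 15% is the SD of change for fMRI, an assumed regional shift of 2% to 5% raises the chance of a significant ROI result from 5% to between 10% and 36% at n = 25. The per-voxel figure for a 5% shift is about 3.6%. Nothing in the documents shows that such a shift will occur.

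The absence of a pre/post test of the meditation-minus-rest difference is a gap in specification. It would be going too far to conclude that adding the test lets the trial attribute changes to the retreat: it cancels only shifts common to both runs. Nor do these passages show that the study needs a control arm for its stated objectives.

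**What to change.** 1. **Section 4.2(c).** Replace the causal wording with *pre-to-post changes associated with participation in the program*, in line with Objectives 1 and 3. State that retreat and repeat-session effects are not separable in this design.
2. **Section 9.1, fMRI.** Add the per-subject contrast (meditation − rest, post) − (meditation − rest, pre) with a one-sample test. Require it for any statement that the response to meditation differed from pre to post, rather than inferring this from one state being significant and the other not. Report it as an association, and say that it cancels only shifts common to both runs. Keep the separate rest and meditation comparisons as pre/post changes.
3. **Section 9.1, SPM.** Clarify that 'groups' means sets of images by session or state, since no second cohort exists. Do not simply delete 'between'.

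**Cost.** Some wording and one extra contrast on runs already planned; no new scans, subjects or staff. The claim becomes more modest. The contrast may be less precise if the two runs correlate weakly, misses changes shared by rest and meditation, and remains biased if the session shift differs between runs.

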4.3 Minimization of Bias

Scans will not be identified by name so that the reviewer can be blinded to the subject's clinical condition. When such blinding cannot be maintained as determined by the principal investigator,

an impartial reviewer who has had no connection with the subject or the subject data will confirm the analysis.

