4.1 Endpoints

DaTSCAN binding changes, and CBF changes, associated with the pre and post meditation program states.

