The traditional method for analyzing brain fMRI and SPECT images involves the ROI method described above. However, it has long been known that ROI definition, particularly on functional images, is time-consuming, subjective and prone to operator bias. Small regular ROI's are capable of resolving localized focal changes between images, although they are subject to a loss of specificity due to the problems associated with multiple comparisons. Alternatively, large ROI's encompassing an entire brain structure may dilute small activation foci, with a subsequent loss of sensitivity. Unless a study is very strongly hypothesis driven, and comparisons between images are only being made in highly specific regions, ROI analysis lacks the power to accurately distinguish regional variations between a set of images. The solution to this problem has been the development of pixel-based statistical analyses, where the regions are effectively reduced to single pixels (Acton 1998). This method can also be utilized to observe changes in structures not included as part of the ROI analysis.

Therefore, SPM2 software (Wellcome Department of Cognitive Neurology, London, UK) will also be performed in which the image volumes of transverse slices will be made compatible with SPM by creation of usable headers for the images. To begin, a file will be created for each image that contains data on image size, number of slices, pixel depth, maximal pixel value, and voxel size. SPM analysis then requires 1) spatial normalization of all images into the same stereotactic space, 2) smoothing, and 3) statistical parametric comparisons. Spatial Normalization will begin by having the scans from each individual subject will be coregistered to each other, using a rigid-body transformation. To correct for global brain shape differences, the individual MRI volume acquisitions will be transformed into a standard 3D space (MNI, provided by SPM). The images will be coregistered to a MNI atlas template, using affine transformations and nonlinear warping ($7 \times 8 \times 7$ basis functions). The resulting spatially normalized images had isotropic voxels of size 2 mm. The normalized images will be smoothed by convolving with an isotropic FWHM 12 mm Gaussian kernel that allows the subsequent voxel-by-voxel analysis. This reduces the effects of image noise and conditions the data for subsequent statistical tests performed in SPM.

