9.5 Procedure for Accounting for Missing, Unused, or Spurious Data

Missing or unused data will be excluded from analysis and reported in the subject's study binder. However, other data from that subject will be included in the analysis where appropriate and also for all safety evaluations. Spurious data will be evaluated by a statistician to determine how such data should be handled from a research reporting perspective. However, any data that is spurious will be provided to the subject's physicians in the event that it provides useful clinical information.

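### Section 4.3 masks the subject's name and clinical condition but states no masking of session, scan date or reading order, although the primary endpoint is a pre/post change measured in manually adjusted regions

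*Combined protocol and SAP*

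**What the plan says.** - **Masking (4.3).** "Scans will not be identified by name so that the reviewer can be blinded to the subject's clinical condition". If the principal investigator decides that this cannot be maintained, "an impartial reviewer who has had no connection with the subject or the subject data will confirm the analysis". Nothing else in the section concerns masking.
- **Population and allocation (2.6, 4.8).** "Subjects will be healthy controls". "Since this is a diagnostic study, subjects are not randomized".
- **Endpoints (4.1).** "DaTSCAN binding changes, and CBF changes, associated with the pre and post meditation program states". Section 4.2(b) names the SERT and DAT binding ratios, ROI against cerebellum, as the primary outcome measure.
- **ROI placement (9.1, Region of Interest Analysis).** "Each ROI will have its placement adjusted manually in order to achieve the best fit according to the atlas". The adjusted ROIs are then copied to the scans. Section 4.2(b) has the template fitted on each MRI and copied to the SPECT images.
- **The plan's own view of ROI definition (9.1, SPM).** It is "time-consuming, subjective and prone to operator bias", which the plan says applies particularly to functional images. The plan offers voxel-wise analysis as the answer and runs it alongside the ROI analysis.
- **Irregular data (9.5).** "Spurious data will be evaluated by a statistician", with no statement of whether the session is hidden at that point.

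**The concern.** A masking rule protects a comparison only if it hides the factor being compared. Here no diagnostic groups or arms are compared, so hiding clinical condition protects little. The DAT and SERT endpoint compares two scans of the same person, and removing a name does not hide which scan came second.

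This matters because the primary ratio depends on where an operator puts the ROIs, cerebellum included. A placement habit that differs on average between pre and post scans would enter the change score directly. With no control group, it could not be told apart from a retreat effect. It need not be intentional: if all baseline scans were processed before all follow-up scans, drift in technique over time would do the same.

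**Working it through.** **1. Does any safeguard in the text hide the session?**

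| Safeguard | Where | What it does | Hides session? |
|---|---|---|---|
| Name removed | 4.3 | Hides identity | Not stated |
| Impartial reviewer | 4.3 | Confirms the analysis, only if the investigator finds that blinding has failed | Not stated |
| ROIs fitted on MRI, then copied | 4.2(b), 9.1 | Keeps placement away from the tracer signal | No, but limits what an operator can influence |
| Two technicians, intra-class correlation above 0.95 | 4.2(b) | Checks agreement | No; two operators who know the session can share a bias |
| Voxel-wise SPM | 4.2(c), 9.1 | Uses no hand-placed ROIs | No; runs beside the ROI-based primary outcome |

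**2. How far does copying the ROIs go?** The order in 9.1 is adjust first, then copy, so manual adjustment is not described as following the copying. Two gaps remain. Section 4.2(b) makes co-registration of SPECT with MRI optional, while 9.1 states it as definite. And MRI is performed at both visits (4.2, 4.5), the template is fitted on each MRI, and neither section requires one ROI set to serve both sessions.

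**3. Size, as an illustration.** The plan gives no figure for reader bias, so there is none to reproduce. Inputs:

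- n = 25 pairs (9.2, 9.4).
- SD = 15% (9.2), taken here as the SD of the within-subject change. This is an assumption: 9.2 speaks of differences or changes and names a two-group t-test.
- Two-sided alpha = 0.05 (9.2), and no true change.
- Systematic post-minus-pre reader shift b = 1% to 5%. This is an assumption with no basis in the documents.

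For a paired t-test the noncentrality is (b / SD) × √n = (b / 15) × 5 = b / 3, with 24 degrees of freedom. The false-positive rate is the probability that a noncentral t with that parameter exceeds the usual two-sided critical value in absolute size.

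| Shift b | Noncentrality (n = 25) | False-positive rate, n = 25 | Same, n = 30 (upper recruitment figure, 5.1) |
|---|---|---|---|
| 0% | 0 | 5.0% | 5.0% |
| 1% | 0.33 | 6.2% | 6.4% |
| 2% | 0.67 | 9.8% | 10.9% |
| 3% | 1.00 | 16.1% | 18.5% |
| 4% | 1.33 | 24.9% | 29.2% |
| 5% | 1.67 | 36.0% | 42.3% |

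For scale, 9.2 expects a change of about 10%, so a 3% shift is 3/10 of the expected effect. A larger SD of change would lower these rates and a smaller one would raise them.

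**The case against.** The strongest reply is that the documents are silent on session; they do not say that readers will know it. In an all-healthy cohort, clinical condition in 4.3 may be loose wording for scan state. If ROIs are placed on anatomical MRI, the operator does not see transporter signal while adjusting, so steering the ratio is hard. The plan's warning about operator bias is aimed mainly at functional images, and its remedy, voxel-wise analysis, is run as well. The objectives state no direction of change, and the illustration needs a shift that runs the same way on average across subjects. The study is also exploratory by its own description.

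Much of this stands. A reader might infer that the technicians are unmasked and that the primary result is therefore biased; the text supports neither. Nor is pre versus post the trial's only comparison: 4.2(c) adds an fMRI contrast of rest with meditation, and correlations with questionnaire measures are planned. CBF change is also assessed by SPM, so ROI placement does not determine it alone.

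The gap itself remains. Even if clinical condition is read as scan state, removing names would not hide it. Protection through the MRI depends on co-registration that one section leaves optional, and on a common ROI set that no section requires.

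**Conclusion.** The point holds as a defect in the masking rule, not as evidence of bias. Section 4.3 specifies masking for a factor that hardly varies in this trial and specifies none for the factor on which the primary endpoint turns. The MRI-based placement and the SPM analysis reduce the exposure without closing it.

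The numerical range, from about 6% at a 1% shift to 36% at a 5% shift, shows sensitivity only. It rests on assumed shifts, a consistent direction across subjects, 25 pairs, and 15% being the SD of change. The point changes no sample size. The correction should be made, since it protects the primary outcome at little cost.

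**What to change.** Reword 4.3 to state that:

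- each scan carries a random code, with name, date and session removed from labels and image headers;
- a subject's scans are processed in random order by the existing technicians, who do not hold the key;
- one MRI-defined ROI set per subject is used for both sessions where feasible;
- all ROI values, and any decision on spurious data under 9.5, are locked before the key is released.

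Bring 4.2(b) and 9.1 into agreement on whether SPECT is always co-registered with the MRI.

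The cost is protocol wording, header anonymization and a code list kept by existing staff. No scan, subject or reader is added.
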